The use of only local anesthetic for this fascial plane abdominal block may not have wide use in this field due to its minimal duration of action after the cessation of neuraxial anesthetic, but if the duration of action could be substantially extended, this technique may become a more common practice to improve patient care and satisfaction.

When combined with local anesthetic in TAP blocks, dexamethasone has the potential to prolong the duration of analgesia following cesarean section. Dexamethasone is well-known for its anti-emetic and anti-inflammatory properties; however, it has also been shown in studies to reduce post-operative pain and increase the duration of regional anesthesia blocks. The dosage required to show significant benefit, however, has not been established with any consistency.

Our study aims to determine if and at what dose does dexamethasone consistently extend the duration of these blocks; thereby, improving post-cesarean section pain.

2.0 **BACKGROUND & RATIONALE**

Recent studies have analyzed the efficacy of TAP blocks for post-surgical analgesia following abdominal procedures, including cesarean sections, with many of these studies showing superior analgesia when compared with infiltrative anesthesia and intravenous post-operative opioids alone (1-5), and they have shown minimal risk to the patients.

Dexamethasone as well has been studied and has shown in several trials to not only help reduce PONV but also to decrease post-cesarean pain in the first 48 hours. A dose of 5mg of dexamethasone has been suggested to be the minimum amount required to achieve the desired results with intravenous medication use (6).

There have been several studies looking at the potential benefits of utilizing dexamethasone as an adjuvant in regional anesthetic blocks to prolong duration of block and subsequently to provide superior post-operative analgesia with minimal side effects (8, 9);

however, there is minimal data on its role and dosage as an adjuvant to TAP blocks following cesarean section (7).

Our study hopes to show that the addition of dexamethasone in bilateral TAP blocks will prolong the duration of the block in a dose-dependent fashion. We will also analyze this data to attempt to show that the prolongation of the block will also decrease post-operative pain, decrease opioid consumption, and improve overall patient satisfaction.

3.0 SIGNIFICANCE OF STUDY

Our study aims to improve the care of the obstetric population after cesarean section and improve total patient satisfaction by improving post-surgical pain control with the use of dexamethasone in combination with bilateral TAP blocks. We will utilize a dose-escalation of dexamethasone in the TAP block to observe its effects at specific small doses. Our hope is that our technique would become utilized routinely for the obstetric population following cesarean section.

4.0 OBJECTIVE(S) & HYPOTHESIS

Purpose: improve post-operative pain following cesarean section, increase duration of TAP block with use of dexamethasone, decrease overall pain scores in the first 24-48 hours, and decrease opioid requirements after cesarean section.

Outline of Therapy:

Primary endpoints or outcomes:

1. Estimation of duration of TAP block, assessed within 48 hours after surgery

Secondary endpoints or outcomes:

1. Pain scores (VAS) at immediate post-op, every 15 minutes in the PACU, then every 6 hours on an inpatient floor until approximately 48 hours post-operatively.
2. Average pain score in first 48 hours
3. Time until first dose post-operative opioid administration
4. Opioid consumption in first 48 hours post-operatively
5. Use of rescue PONV medications (i.e. ondansetron, promethazine)
6. Patient satisfaction

Study Hypothesis: Dexamethasone will demonstrate a significant increase in duration of TAP block in a dose-dependent fashion when compared with local anesthetic alone.

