After completion of the procedure, the patients will receive bilateral TAP block procedure while still in OR. All blocks will include 20mL of 0.5% ropivacaine, and the patients will be randomly assigned a specific dose of dexamethasone at 0mg (given normal saline as control), 2mg, or 4mg respectively. The resident or attending physician supervising the block will be investigators in the study, and they along with the residents performing the blocks will be blinded to the amount of dexamethasone in the injectate.

Postoperatively: The patients will then be monitored in the PACU for approximately 30-60 minutes and then subsequently monitored on an inpatient floor. Pain scores, time until first opioid dose, total opioid requirement will be assessed and recorded. In PACU, these will be recorded every 15-30 minutes. On the inpatient floor, these will be recorded every 6 hours. Satisfaction scores and estimation of TAP block duration will be assessed and recorded by anesthesia personnel approximately 24 hours post-operatively.

Measured Endpoints: VAS scores every 15-30 minutes while in PACU then recorded every 6 hours on the floor for 48 hours; time until first doses of opioid, opioid requirement in first 48 hours, subjective patient satisfaction, and estimation of block duration.

Projected Overall Study Timeline

Aug 2015 - Feb 2016	Mar 2016 – Dec 2016	Jan 2017 – Feb 2017	Mar 2017
Study Start-Up			
	Enrollment		
		Data Entry and Analysis	
			Study Write-Up

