9.0 STATISTICAL CONSIDERATIONS

Demographic Variables: Patient age, BMI, co-morbidities.

Control Variables: Dexamethasone dose (0 mg, 2 mg, or 4 mg).

Primary Study Variables: The primary endpoint for this study is the duration of TAP block. This endpoint will be assessed within 48 hours post-surgery.

General Data Analysis: All demographic and clinical variables with continuous measures will be expressed as means and standard deviations; categorical factors will be expressed as proportions. For non-normal data, the medians and inter quartile ranges will be displayed. The distribution of the continuous factors will be examined using the Kolmogorov-Smirnov test. For data that are normally distributed, one-way ANOVA will be used to compare groups of data. For data that are not normally distributed, the Kruskal-Wallis test will be used for comparisons. Chi-square and Fisher's exact tests will be used to analyze categorical data. For all comparisons, a value of $p < 0.05$ will be considered statistically significant.

Primary Outcome Analysis: Statistical analyses will be performed using SAS for Windows, version 9.2. One-way ANOVA (or the Kruskal-Wallis test, as appropriate) will be used to compare duration of TAP block for the three groups. Linear regression will also be used to test the relationship between duration of block and dexamethasone dose, while controlling for relevant clinical and demographic variables.

Secondary Outcome Analysis: One-way ANOVA (or the Kruskal-Wallis test) will be used to compare the groups on post-operative pain scores, opioid requirements, and patient satisfaction scores.

Additional Data Analysis: N/A

Statistical Power and Sample Size Estimates: Approximately 69 subjects (23 per group) are expected to be enrolled in this study. Given this sample size and assuming that the average duration of TAP block is 18 hours for the control group, 22 hours for the 2 mg of dexamethasone group, and 24 hours for the 4 mg of dexamethasone group, this study will have approximately 80.9% power to detect a difference in block duration, assuming a common standard deviation of 6 hours. If the variability in block time is smaller than 6 hours, this study will have greater power.

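### The primary endpoint, block duration, has no start time, end event or question, and is collected as one look-back estimate at about 24 hours, before many blocks would have ended

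*Combined protocol and SAP*

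**What the plan says.** Section 4.0 names the primary endpoint as "Estimation of duration of TAP block, assessed within 48 hours after surgery". Section 9.0 repeats the name and the window: "This endpoint will be assessed within 48 hours post-surgery". Section 8.0 describes the collection, in both the study design text and the postoperative text: "Satisfaction scores and estimation of TAP block duration will be assessed and recorded by anesthesia personnel approximately 24 hours post-operatively".

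No section gives a starting point, an end event, a question or an instrument. Time to first opioid cannot serve as an implied definition, because Section 4.0 lists it as a separate secondary endpoint.

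Section 8.0 also sets up a repeated floor record. Its content is described as "Pain scores, time until first opioid dose, total opioid requirement will be assessed and recorded", its frequency as "On the inpatient floor, these will be recorded every 6 hours", and its length under the measured endpoints as "VAS scores every 15-30 minutes while in PACU then recorded every 6 hours on the floor for 48 hours". Block status is not among the items recorded.

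**The concern.** The hypothesis and the sample size both rest on this one variable, in hours. The clock could start at the end of injection, the end of surgery or the wearing off of the spinal. It could stop at return of abdominal-wall sensation, return of incisional pain or the first opioid. Because all patients receive spinal bupivacaine and 0.1 mg intrathecal morphine (Section 8.0), these choices may give answers hours apart in the same patient. If the choice is left to whoever makes the visit, or to the patient, the recorded figure can mix several quantities, and it cannot be fully separated again at analysis.

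The timing adds to this. A single visit can only look back on blocks that have already ended, and it cannot see the end of blocks that are still working. Sections 4.0 and 9.0 (within 48 hours) and Section 8.0 (about 24 hours) give different timings. Moving the one visit to 48 hours would remove most of the second problem, but it would lengthen recall and leave the definition open.

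**Working it through.** **1. The plan's own power figure.** Inputs from Section 9.0: "Approximately 69 subjects (23 per group) are expected to be enrolled in this study"; means 18, 22 and 24 h; common SD 6 h; "For all comparisons, a value of $p < 0.05$ will be considered statistically significant"; one-way ANOVA on three groups.

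- Grand mean = (18 + 22 + 24)/3 = 21.33 h.
- Sum of squared deviations = 11.11 + 0.44 + 7.11 = 18.67.
- Noncentrality λ = 23 × 18.67 / 6² = 11.93, with 2 and 66 degrees of freedom.
- Power from the noncentral F distribution = **86.5%**.

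The stated 80.9% is not reproduced at 23 per group. It matches 20 per group (80.86%), so an unstated 15% overage (60 × 1.15 = 69) may explain it. That is a separate matter. Below, 86.5% is a recalculated baseline, not the plan's figure.

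**2. Blocks still working at a 24-hour visit.** Assuming normal durations with the plan's means and SD, the share beyond 24 h is 1 − Φ((24 − mean)/6).

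| Arm | (24 − mean)/6 | Share beyond 24 h | Expected of 23 |
|---|---|---|---|
| 0 mg | 1.00 | 16% | 3.6 |
| 2 mg | 0.33 | 37% | 8.5 |
| 4 mg | 0.00 | 50% | 11.5 |

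That is about 24 of 69 patients. Beyond 48 h the share is below 0.01% in every arm.

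The plan does not say what is recorded for a block still working at the visit. If 24 h were entered for these patients, simulation (20,000 runs) gives mean recorded durations of 17.5, 20.5 and 21.6 h. The difference between 4 mg and control would shrink from 6 h to 4.1 h, and ANOVA power would be about 81.8%.

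**3. Noise from mixed definitions or recall (illustration).** Let e be the SD of independent added error, and assume that the plan's 6 h contains none of it. Total SD = √(36 + e²). The documents give no value for e.

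| e (assumed) | Total SD | λ | Power, 23 per group |
|---|---|---|---|
| 0 h | 6.00 h | 11.93 | 86.5% |
| 2 h | 6.32 h | 10.73 | 82.6% |
| 3 h | 6.71 h | 9.54 | 77.6% |
| 4 h | 7.21 h | 8.26 | 71.1% |

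Power falls below 80% once e exceeds about 2.6 h.

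**4. Cost of reading the endpoint at 6-hourly checks.** Reading only to a 6-hour grid adds SD 6/√12 = 1.73 h, so total SD = √39 = 6.24 h and power is about 83.5% by formula. Simulation gives 83.7% to 84.1% for ANOVA. For Kruskal-Wallis the simulated figures are 84.5% without a grid and about 82% with it.

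**The case against.** **The power loss is not established.** This stands. Section 9.0 gives no source for the 6 h SD. If it came from durations estimated in a similar way, some or all of the error is already in it. At e = 2 h, power is still above the stated 80.9%. A reader might infer that the trial is underpowered because of this endpoint; the documents do not support that.

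**Blinding protects the comparison.** This also stands. Section 8.0 describes the study as double-blind, so inconsistent definitions would mainly add noise. A reader might infer that the result favours one arm, but nothing in the plan points that way. Nor do the documents say how many people make the assessments, so variation between assessors is an inference.

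**Other data allow a cross-check.** In part. Pain scores and time to first opioid are recorded separately and can be set against the estimated durations. It would therefore go too far to call the primary result unreadable. But these data measure other things and cannot restore a duration whose definition was never fixed.

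**Prospective checks may not gain power.** Fair. The grid error of 1.73 h is close to the lower assumed recall error of 2 h, and a clock time given between checks still relies on short recall. The case for the checks is a defined, observable endpoint, not a promised gain in power.

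**A pain-based end event has its own weakness.** True: intrathecal morphine may mask returning pain, so pain alone may not isolate the block. That bears on which event to choose, and is a reason for the investigators to choose one explicitly.

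**Conclusion.** The concern holds as a gap in definition and timing. The plan does not say what block duration is, and it collects it at one visit which, on its own assumptions, falls before the end of 16%, 37% and 50% of blocks. Those shares rest on normal durations with the plan's means and SD, and on the 24-hour timing in Section 8.0 rather than the 48-hour window in Sections 4.0 and 9.0.

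The direction of any effect on power is downward, but its size is unknown. The illustrated range of 82.6% to 71.1% depends wholly on assumed error of 2 to 4 h on top of an error-free 6 h SD. The lasting consequence is for interpretation: without a definition, a difference in hours cannot be tied to one event or repeated by another group. This should be put right before enrolment, because mixed records cannot be fully repaired afterwards.

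**What to change.** Before enrolment, amend Sections 4.0, 8.0 and 9.0 together:

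- **Start:** one fixed time, for example completion of the second-side injection.
- **End:** one event, chosen by the investigators (return of abdominal-wall sensation, or return of incisional pain), with a written rule for the analysis of opioid taken before that event.
- **Collection:** one scripted question at each existing 6-hourly floor check to 48 hours, noting the clock time of the event. The visit at about 24 hours can remain for satisfaction.
- **Analysis:** rank any block still working at 48 hours highest, and name the already planned Kruskal-Wallis test as the primary test, in place of a choice made after a normality test. On the plan's assumptions almost no block would last that long.
- **Consistency:** reconcile the 24- and 48-hour statements for the primary endpoint. Check also that the 18, 22 and 24 h means and the 6 h SD apply to the event chosen.

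The cost is one added item in the floor record, a little nursing time and a short script, with no new visits. A pure 6-hour reading would cost about 3 power points (86.5% to about 83.5% for ANOVA; 84.5% to about 82% for Kruskal-Wallis), and less if clock times are recorded.

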5.0 INTERPRETATION OF EXPECTED RESULTS

We expect our results to confirm our hypothesis that post-operative bilateral TAP blocks with dexamethasone will show a significant increase in duration of TAP block in a dose-dependent fashion; thus it will show an overall improvement in post-operative pain in the first 48 hours following cesarean section.

6.0 ELIGIBILITY & EXCLUSION CRITERIA**Eligibility criteria:**

1. Women, 18 years and older, undergoing elective cesarean section delivery.
2. Patients classified as American Society of Anesthesiology class II or III.
3. Spinal anesthesia utilized as intra-operative anesthesia for cesarean section.

Exclusion criteria:

1. Any patient not classified as an ASA II or III.
2. General Anesthesia or neuraxial anesthesia with epidural used as anesthetic techniques for cesarean section.
3. Emergency cesarean sections.
4. Allergy/intolerance to local anesthetic or steroids.
5. Pre-existing neurological and/or anatomical deficit that would preclude regional block.
6. Coexisting coagulopathy such as hemophilia or von Willebrand Disease.
7. BMI > 40.
8. History of intravenous drug or opioid abuse.
9. History of opioid use within a week prior to cesarean section.
10. History of any chronic pain syndrome.

7.0 RANDOMIZATION/RECRUITMENT PROCEDURES

Recruitment: Participants will be recruited, identified, and interviewed by either the study Principal Investigator or one of the co-investigators. The interviewing investigator will confirm eligibility and the absence of any exclusionary criteria. Details of the study (including risks) will be explained to prospective participants to their satisfaction and consent forms will then be signed.

Randomization: Upon enrollment into the study, participants will be randomized to three groups all which will receive bilateral TAP blocks but the addition of either 2 mg (Group 1) or 4 mg (Group 2) or 0 mg (Control Group) of dexamethasone to the ropivacaine used to perform the TAP block. Randomization will be performed using a random number generator.

8.0 STUDY INTERVENTIONS/PROCEDURES**Study design.**

This study is a prospective study, placebo-controlled, double-blinded investigation of the effect of adjuvant dexamethasone in bilateral transverse abdominal plane blocks to prolong the abdominal fascial plane block. Patients undergoing C-section will be screened pre-operatively for inclusion/exclusion criteria. These patients will receive as the standard-of-care neuraxial anesthesia in the form of a spinal anesthetic with bupivacaine for intra-operative pain control, as well as given 0.1mg of intrathecal morphine for post-operative pain control. The patients will then be treated with bilateral

post-operative TAP blocks. This will be a 3-armed study, with each arm receiving the same dose of local anesthetic, 20mL 0.5% ropivacaine, and a different dose of dexamethasone in the block. The patients will receive 0mg (Control Group), 2mg (Group 1), or 4mg (Group 2) of dexamethasone total in bilateral blocks by the anesthesia team in the OR. The dose of dexamethasone will be split between the two sides of the block. Post-operative use of pain medication, pain scores, time until first opioid dose, and opioid requirement in the first 24 hours by the PACU and floor nurses, and these will be recorded in the electronic medical record. Satisfaction scores and estimation of TAP block duration will be assessed and recorded by anesthesia personnel approximately 24 hours post-operatively.

Comparison groups.

The Control Group, as noted above, will also receive spinal anesthetic with bupivacaine and intrathecal morphine and then post-operative bilateral TAP blocks. The same post-operative measures will be obtained from this group as from the Groups 1&2.

Study and timeline of interventions.

Preoperatively: informed consent will be obtained by a member of this study. The patients will be screened for inclusion/exclusion criteria on day of procedure, and then they will be randomized to one of three groups.

Intraoperatively: The anesthesia team involved with care of patient in the operating room will provide routine anesthesia care during the cesarean section including neuraxial anesthesia with intrathecal bupivacaine and morphine.

After completion of the procedure, the patients will receive bilateral TAP block procedure while still in OR. All blocks will include 20mL of 0.5% ropivacaine, and the patients will be randomly assigned a specific dose of dexamethasone at 0mg (given normal saline as control), 2mg, or 4mg respectively. The resident or attending physician supervising the block will be investigators in the study, and they along with the residents performing the blocks will be blinded to the amount of dexamethasone in the injectate.

Postoperatively: The patients will then be monitored in the PACU for approximately 30-60 minutes and then subsequently monitored on an inpatient floor. Pain scores, time until first opioid dose, total opioid requirement will be assessed and recorded. In PACU, these will be recorded every 15-30 minutes. On the inpatient floor, these will be recorded every 6 hours. Satisfaction scores and estimation of TAP block duration will be assessed and recorded by anesthesia personnel approximately 24 hours post-operatively.

Measured Endpoints: VAS scores every 15-30 minutes while in PACU then recorded every 6 hours on the floor for 48 hours; time until first doses of opioid, opioid requirement in first 48 hours, subjective patient satisfaction, and estimation of block duration.

Projected Overall Study Timeline

Aug 2015 - Feb 2016	Mar 2016 – Dec 2016	Jan 2017 – Feb 2017	Mar 2017
Study Start-Up			
	Enrollment		
		Data Entry and Analysis	
			Study Write-Up

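### Dexamethasone dose in the block is the only experimental variable, but the plan neither restricts systemic corticosteroid outside the block nor lists it among the data to collect

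*Combined protocol and SAP*

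**What the plan says.** Section 8.0 (Study design) holds the ropivacaine, spinal bupivacaine and 0.1 mg intrathecal morphine constant and varies only the dexamethasone in the block. The study hypothesis in section 4.0 sets dexamethasone against local anesthetic alone.

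Other care is left open. Under Intraoperatively, section 8.0 says the team "will provide routine anesthesia care during the cesarean section including neuraxial anesthesia with intrathecal bupivacaine and morphine".

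Steroids or anti-emetics come up in four other places:
- The opening text says "Dexamethasone is well-known for its anti-emetic and anti-inflammatory properties".
- Section 2.0 says the drug "has shown in several trials to not only help reduce PONV but also to decrease post-cesarean pain in the first 48 hours" and reports 5 mg as the suggested minimum effective intravenous dose.
- Section 4.0 lists as a secondary outcome "Use of rescue PONV medications (i.e. ondansetron, promethazine". This defines an outcome; it is not a rule on which anti-emetics may be given.
- Section 6.0 excludes "Allergy/intolerance to local anesthetic or steroids", but not prior or concurrent steroid use.

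The Measured Endpoints in section 8.0 are "VAS scores every 15-30 minutes while in PACU then recorded every 6 hours on the floor for 48 hours", time to first opioid, and "opioid requirement in first 48 hours, subjective patient satisfaction, and estimation of block duration". Section 9.0 adds age, BMI and co-morbidities and gives the assigned dose as the only control variable. Non-study corticosteroid is on none of these lists.

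**The concern.** The plan controls the study drug inside the block and leaves it uncontrolled outside. By the plan's own account this drug is a well-known anti-emetic that also lessens post-cesarean pain over the first 48 hours, which is when pain and opioid use are measured. A woman in the 0 mg arm could be given dexamethasone for nausea and remain fully within protocol. If she received the 5 mg mentioned in section 2.0, her total would exceed the 4 mg that Group 2 receives from the block, though by a different route.

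Such exposure would pull the arms together or add variability. The most direct effect would be on pain, opioid use and rescue PONV medication, because the systemic evidence cited in the plan concerns pain and PONV. An effect on block duration, the primary outcome, is an assumption. Exposure after the block could also depend on the arm, for example if an arm with more nausea were given more anti-emetics, so it should be visible by arm. A weak or flat dose-response would be hard to interpret if exposure to the same drug could not be ruled out from the planned data.

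**Working it through.** **Inputs from section 9.0:** 23 per group; mean durations 18, 22 and 24 h; common SD 6 h; significance level 0.05; three-group one-way ANOVA.

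**Inputs the documents do not give, taken as assumptions:** *f*, the share of each arm given non-study systemic dexamethasone (the same in all arms); *s*, the fraction of the gap to the best arm's mean (24 h) that an exposed patient gains.

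**Step 1: the plan's own figure.** The grand mean is 21.33 h and the sum of squared deviations is 18.67. The noncentrality is λ = 23 × 18.67 / 36 = 11.93. With 2 and 66 degrees of freedom, power is 86.5%, against the stated 80.9%. The stated figure matches 20 per group (λ = 20 × 18.67 / 36 = 10.37, power 80.9%), or a Kruskal-Wallis allowance at efficiency 0.864 with 23 per group. The text states neither. The difference is on the conservative side and is a separate matter. The baseline below is 86.5%.

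**Step 2: exposed patients move towards the best arm.** Gain g = s × (24 − arm mean). Arm mean becomes mean + f × g. Arm variance becomes 36 + f(1 − f)g², averaged over arms.

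Example, s = 1 and f = 0.10: means 18.6, 22.2 and 24.0; sum of squares 15.12; average variance 37.2; λ = 23 × 15.12 / 37.2 = 9.35; power 76.7%.

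| Assumed effect | f = 5% | f = 10% | f = 20% | f at which power is 80% |
|---|---|---|---|---|
| s = 0 (none on duration) | 86.5% | 86.5% | 86.5% | never |
| s = 0.25 | 85.6% | 84.6% | 82.5% | 31% |
| s = 0.5 | 84.5% | 82.3% | 77.5% | 15% |
| s = 1 | 82.0% | 76.7% | 64.8% | 7% |

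At f = 10% the difference between 4 mg and 0 mg is 6 × (1 − 0.10s): 5.85, 5.7 and 5.4 h for s = 0.25, 0.5 and 1, against 6 h with no exposure.

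**Step 3: exposed patients gain the same number of hours in every arm.** The mean differences stay as planned and only the variance grows, to 36 + f(1 − f) × shift².

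| Shift | f = 5% | f = 10% | f = 20% |
|---|---|---|---|
| +3 h | 86.1% | 85.7% | 85.1% |
| +6 h | 84.8% | 83.3% | 80.8% |

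**Step 4: secondary outcomes.** The plan gives no effect size or SD for these, so only a scale-free statement is possible. Under the Step 2 model a difference between arms keeps a fraction 1 − s × f of its size, and the sample needed for the same power grows by 1/(1 − s × f)², ignoring the extra variance. At f = 10%, s = 0.5 keeps 95% (1.11 times the patients) and s = 1 keeps 90% (1.23 times). At f = 20%, these become 90% (1.23 times) and 80% (1.56 times).

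**The case against.** The strongest reply is that both links are unknown: no section says systemic dexamethasone is used at this site, and none says it alters block duration. Patients are randomised, and those who supervise and perform the block are blinded to its content. The large losses need s = 1, a ceiling at 24 h that nothing in the plan supports; under a common shift, power stays near 81% or above up to 20% exposure. All of this stands, and it limits the point to a cheap improvement.

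It can also be said that the rescue outcome names two non-steroid drugs and would probably count a steroid given as rescue. That is a partial answer. The outcome does not cover prophylaxis or other steroid use, and it forbids nothing. Post-operative pain medication and opioid data go to the chart ("these will be recorded in the electronic medical record"), the data sheets are not shown, and the regression in section 9.0 leaves its clinical covariates unnamed. Exposure may therefore be recoverable later, but a later look cannot prevent it.

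A third reply is that adding block dexamethasone to usual care is a legitimate pragmatic question. That fits poorly with a hypothesis whose comparator is local anesthetic alone.

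A reader might infer more than the documents support:
- *The comparison is biased.* Exposure before the block cannot depend on a blinded, random allocation. Chance imbalance with 23 per arm is possible, and the listed data would not show it, but that is not systematic bias.
- *Contamination will occur, or the trial is underpowered because of it.* No exposure rate or effect is given.
- *Exposed patients would be dropped.* Section 9.0 proposes no such exclusion, so no correction is needed there.

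**Conclusion.** The gap is real. The plan permits the study drug by another route in any arm, and does not list it for collection, although its own background says the drug acts on outcomes the trial measures. The consequence is a possible dilution of the dose contrast and extra noise, most direct for pain, opioid use and rescue PONV medication.

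The size is not fixed by the documents. At 5% exposure, none of the models tried costs more than 86.5 − 82.0 = 4.5 points of power on the primary outcome. At 20%, the result runs from no loss (s = 0) to 64.8% power (s = 1). These figures only illustrate the stated assumptions and do not forecast the trial's power. The change is worth making because it is cheap and protects the stated comparison.

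**What to change.** 1. In section 8.0, after the Intraoperatively sentence, add: *From arrival for surgery to 48 h after surgery, no non-study systemic corticosteroid is given in any arm unless medically required; non-steroid anti-emetics such as ondansetron or promethazine are used.*
2. In section 8.0, Measured Endpoints, add: *Drug, dose, route and time of any non-study systemic corticosteroid from arrival for surgery to 48 h after surgery, tabulated by arm.*

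The cost is one care rule, one data field and one table. Sample size, arms and the primary test do not change. The downside is a slight limit on anti-emetic choice, softened by the medical exception. If systemic steroid is rarely used at this site the gain is small, but the table would document that.

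### Block duration has only a 24-hour reading scheduled; if that is the last one, up to half of the blocks have no observed end and the dose effect is understated

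*Combined protocol and SAP*

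**What the plan says.** The protocol and SAP are one document. Section 8.0 gives the timing of the primary measurement twice, under Study design and under Postoperatively, in the same words: "Satisfaction scores and estimation of TAP block duration will be assessed and recorded by anesthesia personnel approximately 24 hours post-operatively". No other reading of block duration is scheduled.

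Section 4.0 defines the primary endpoint as "Estimation of duration of TAP block, assessed within 48 hours after surgery", and section 9.0 (Primary Study Variables) says "This endpoint will be assessed within 48 hours post-surgery".

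The Measured Endpoints paragraph of section 8.0 lists "VAS scores every 15-30 minutes while in PACU then recorded every 6 hours on the floor for 48 hours". It names block duration in the same list without a time, so the 48 hours there belongs to the pain scores.

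Section 9.0 compares the three groups on duration by one-way ANOVA or Kruskal-Wallis, and adds: "Linear regression will also be used to test the relationship between duration of block and dexamethasone dose". The sample-size paragraph assumes means of 18 h (control), 22 h (2 mg) and 24 h (4 mg), with a common SD of 6 h and 23 patients per group. It concludes: "24 hours for the 4 mg of dexamethasone group, this study will have approximately 80.9% power to detect a difference in block duration".

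The document does not say how duration is to be estimated, or what is recorded when the block has not worn off by the visit.

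**The concern.** The only scheduled reading falls at the mean duration the plan expects in the 4 mg arm. A visit at that time can record the end of a block only if the end has already happened. On the plan's assumptions, that fails for half of the 4 mg patients and for far fewer controls.

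The hypothesis in section 4.0 is that duration rises with dose. Incomplete readings that become more common with dose act directly on that question: they shrink both dose effects and flatten the step from 2 to 4 mg. The risk is an understated or missed dose response, not a false positive. End times that were never collected cannot be recovered at the analysis stage.

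**Working it through.** **Inputs** (section 9.0): means 18, 22 and 24 h; SD σ = 6 h; 23 per arm; two-sided 5% level. Visit time c = 24 h (section 8.0). Two assumptions are added. Durations are normal, since the plan gives only means and an SD. The word approximately is taken to cover a visit between 22 and 28 h.

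**1. The plan's power figure.** The grand mean is 21.33 and the squared deviations sum to 18.67, so λ = 23 × 18.67 / 36 = 11.93. With 2 and 66 degrees of freedom, ANOVA power is 86.5%, not the stated 80.9%. The stated figure appears with 20 evaluable patients per arm, an allowance the plan does not mention. The stated figure is conservative, and nothing below depends on it. The baseline used here is 86.5%.

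**2. Blocks still working at the visit.** P(X > c) = 1 − Φ(a), with a = (c − μ)/σ.

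| Visit | 0 mg | 2 mg | 4 mg | Patients of 69 |
|---|---|---|---|---|
| 22 h | 25.2% | 50.0% | 63.1% | about 32 |
| 24 h | 15.9% | 36.9% | 50.0% | about 24 |
| 28 h | 4.8% | 15.9% | 25.2% | about 11 |
| 48 h | under 0.01% | under 0.01% | under 0.01% | 0 |

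At 24 h the expected counts are 3.6 + 8.5 + 11.5 = 23.6. Lognormal durations with the same means and SD give 15%, 32% and 45%.

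**3. Ongoing blocks entered as the visit time.** E[min(X, c)] = μΦ(a) − σφ(a) + c(1 − Φ(a)). At c = 24:
- 0 mg: 18 × 0.8413 − 6 × 0.2420 + 24 × 0.1587 = 17.50
- 2 mg: 22 × 0.6306 − 6 × 0.3774 + 24 × 0.3694 = 20.47
- 4 mg: 24 × 0.5 − 6 × 0.3989 + 24 × 0.5 = 21.61

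**4. Ongoing blocks left out.** E[X | X < c] = μ − σφ(a)/Φ(a). At c = 24 the means are 16.27, 18.41 and 19.21.

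**5. Effects and power** (ranges are for a visit at 22 h to 28 h; power for the last two columns is simulated).

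| | Complete | Entered as visit time | Left out |
|---|---|---|---|
| 4 mg minus 0 mg | 6.0 h | 4.1 h (3.4 to 5.2) | 2.9 h (2.4 to 4.1) |
| 2 mg minus 0 mg | 4.0 h | 3.0 h (2.5 to 3.6) | 2.1 h (1.8 to 2.9) |
| 4 mg minus 2 mg, 24 h visit | 2.0 h | 1.1 h | 0.8 h |
| ANOVA power | 86.5% | 82% (78% to 86%) | about 37% (24% to 64%) |

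With equal arms at 0, 2 and 4 mg, the unadjusted regression slope is the 4 mg effect divided by 4. It falls from 6.0/4 = 1.50 to 4.11/4 = 1.03 h per mg (0.85 to 1.30) when ongoing blocks are entered as the visit time. In simulation, the 95% confidence interval for the 4 mg effect, with the SD pooled over the three arms, then contains the true 6 h 69% of the time (36% to 92%).

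**The case against.** A visit at 24 h does fall within 48 h, so the sections do not strictly contradict each other. Staff might intend to complete ongoing blocks later, while patients are still under 6-hourly observation; on that reading there is no bias. The bias requires that 24 h is the last reading, that only an end already reached is recorded, and that ongoing blocks are entered as 24 h or dropped. The plan states none of these. The endpoint is described as an estimate, and an assessor could project an end beyond the visit.

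The planned tests also hold up fairly well if values are capped. ANOVA power of 82% is above the stated 80.9%, and the unadjusted linear dose test keeps 88.0% against 91.5% with complete data. The SD shrinks along with the effect. The plan sets no effect-size target and mentions no confidence interval.

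Much of this stands. The defect is an open schedule and a missing rule, and the size of the bias is conditional. The serious loss of power arises only under exclusion, which the plan does not propose. But no scheduled procedure requires later follow-up, and ad hoc follow-up could differ between patients. A projected end is not an observed duration. Preserved power does not rescue an estimate that is about a third too small, in a trial meant to show how duration depends on dose.

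**Conclusion.** The concern holds. As written, the schedule can cut off the primary endpoint at the 4 mg arm's own planned mean, with no rule for the blocks affected. If 24 h is the last reading, about a third of patients (about 24 of 69) have no observed end. The 4 mg effect is then understated by 1.9 h of 6.0 h if they are entered as 24 h, and by 3.1 h if they are left out.

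These sizes rest on normal durations with the plan's means and SD. The lognormal check lowers the proportions slightly and leaves the pattern unchanged. A later visit reduces the problem: at 28 h the 4 mg effect is 5.2 h and interval coverage is 92%. Follow-up to 48 h removes it. Because the missing end times cannot be recovered afterwards, the point should be settled before recruitment.

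**What to change.** - **Schedule.** Reconcile sections 4.0, 8.0 and 9.0 so that duration is ascertained up to 48 h. Keep the 24-hour visit.
- **Definition and rule.** State how the end of a block is determined. Record a block still working at 24 h as ongoing, not as 24 h and not as missing, and obtain its end by 48 h. Use the same question and definition in all arms. Preferably the same blinded anesthesia personnel ask again; if the 6-hourly floor checks are used, give the nurses the same scripted question.
- **Ends known only to within 6 h.** Fix the rule in advance. Taking ends before 24 h as exact, the interval midpoint gives a 4 mg effect of 6.1 h, power of 85.8% (86.8% with exact times in the same simulation) and 95% coverage. Using the time of the check that finds the block ended gives 7.1 h, an overstatement.
- **Analysis.** Keep the planned ANOVA and regression as primary. Add one sensitivity analysis by parametric regression that treats late ends as interval-censored, and any block ongoing at the last reading as right-censored. The second case should be rare.

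The cost is a wording amendment, a repeat question for about 24 patients (11 to 32), brief training if nurses ask it, and one extra analysis. No extra patients are needed. The downside is up to 6 h of imprecision in late ends and a possible change of assessor. Earlier ends would still rest on recall at the 24-hour visit, so precision would differ between short and long blocks.

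The same amendment can settle a separate mismatch: section 8.0 refers to "opioid requirement in the first 24 hours by the PACU and floor nurses", while section 4.0 lists "Opioid consumption in first 48 hours post-operatively".
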